## 5.3 LIFESTYLE CONSIDERATIONS

Not applicable

## 5.4 SCREEN FAILURES

Screen failures are defined as participants who consent to participate in the clinical trial but are not subsequently randomly assigned to the study intervention or entered in the study. A minimal set of screen failure information is

required to ensure transparent reporting of screen failure participants, to meet the Consolidated Standards of Reporting Trials (CONSORT) publishing requirements and to respond to queries from regulatory authorities. Minimal information includes demography, screen failure details, and eligibility criteria.

Individuals who do not meet the criteria for participation in this trial (screen failure) because of subsequent hemoglobin assessments which prove exclusionary (i.e. hemoglobin > 10 g/dL) may be rescreened as long as they remain in the ICU with a duration not to exceed 7 days at the time of enrollment. Rescreened participants should be assigned the same participant number as for the initial screening.

## 5.5 STRATEGIES FOR RECRUITMENT AND RETENTION

Recruitment: Trained study coordinators from the Anesthesia Clinical Research Unit will receive daily electronic alerts notifying them of Mayo Clinic Rochester ICU patients  $\geq$  18 years of age with a most recent hemoglobin value <10 g/dL (infrastructure for these near real-time electronic alerts [2-5 minute delay] are already in place through the ICU DataMart). Patients may be present in any adult ICU. These patients will then be screened through Electronic Health Record (EHR) review by study staff to ascertain eligibility in accordance with inclusion/exclusion criteria. Patients meeting inclusion/exclusion criteria will be approached by study coordinators in their patient room, or by telephone if indicated based on current clinical and/or IRB policies in the setting of COVID-19-related clinical practice/research modifications. Study coordinators will meet with patient or their legal proxies in the case of a patient's inability to directly communicate with study personnel (i.e. deep sedation). The study coordinator will review the research study in detail, explaining the purpose of the study including iron and erythropoietin administration, additional necessary phlebotomy and needed follow up post hospital dismissal. It will be made clear that all participants will receive routine clinical care regardless of whether they 1) agree to participate in the trial, or 2) are randomized to the active treatment arm. The informed consent discussion will occur between the patient and a member of the study team at the patient's bedside during ICU admission as soon as the patient meets eligibility criteria (i.e. within 24 hours). The patient/proxy will be allowed time to have all their questions answered and assure no exclusions to enrollment are identified. Written informed consent will be obtained by study staff with specific training in this procedure. Signed consent forms will be scanned into the patient's HER and a copy will be provided to the study participant. No information will be used from patients that have not given consent to use their medical information. In the event the LAR consents on behalf of the subject, the study coordinator will make sure and visit with the subject once functional status is reestablished to assure the subject wants to continue with participation. By this time, the subject may/may not have already received study drug, so all they would be affirming is their willingness to continue with the follow up visits/labs/questionnaires.

Retention: A high-level of patient follow-up (>75%) is necessary for success, including in-person evaluations for hemoglobin laboratory draws. To achieve this, we have limited the study to residents residing locally (i.e. patients that receive routine medical cares in Mayo Clinic Rochester or the regional Mayo Clinic Health System), a unique population with a high-level of community engagement in clinical research and a high-level of post-hospitalization medical cares obtained primarily at the Mayo Clinic and its affiliated regional sites. Similar studies of Olmsted County residents, including those with laboratory draws, have achieved >90% retention. Additionally, we are partnering with the Mayo Clinic ICU Rehabilitation Program (MCIRP). The MCIRP is a post-ICU clinic staffed by a physician, advanced ICU care nurse practitioner, ICU pharmacist, and occupational therapist, with the recent addition of a nurse coordinator. In the current care model, survivors of critical illness, identified through real-time electronic data "sniffers", and their family members are approached by MCIRP team members for recruitment prior to hospital discharge. Patients are evaluated within 6 months of hospital discharge with a less than 5% no-show rate for enrolled participants and greater than 90% retention for additional visits. Multi-domain functional outcomes (physical, cognitive, mental health, quality of life) are assessed at each study visit in accordance with the NHLBI-funded improveLTO Core Outcome Measure Set (<http://improvelto.com>). Of note, with COVID-19 precautions, most MCIRP visits have been moved to virtual visitations. We will work with the MCIRP to ensure appropriate follow-up of all enrolled patients. Our goal remains in-person evaluations for all study participants in an outpatient setting. Of note, all core functional outcomes can be assessed over

the phone with exception of 6MWD. *Additional* retention in this clinical trial will be facilitated through employment of published cohort retention tools for longitudinal post-hospitalization critical care outcomes research

[REDACTED] which have resulted in >90% cohort retention through 12 months. This includes utilization of a defined cohort retention protocol, careful collection of multiple unique sources of patient contact including proxies, frequent patient engagement, reminder notifications (e.g. reminder phone calls starting 2 weeks before each follow-up appointment and subsequently a phone call 1 week and 1 day before the *appointment*), remuneration (i.e. \$25 per follow-up visit – 1 month and 3 months post-hospitalization), and vouchers for parking (4-hour parking passes, given at each follow-up visit). Recognizing that some patients may die or be lost to contact prior to outcome assessment (~25%), we have increased our study sample size from 74 to 100 participants.

## 6 STUDY INTERVENTION

### 6.1 STUDY INTERVENTION(S) ADMINISTRATION

#### 6.1.1 STUDY INTERVENTION DESCRIPTION

The intervention arm is multi-faceted with 3 primary components:

- 1) **Optimized phlebotomy**, defined by minimal volume draws (i.e. 0.1-2 ml vs. standard 3-10 ml per laboratory order) and closed-loop blood sampling, all performed by a dedicated phlebotomy team independent from the treatment team. This intervention simply requires communication with the phlebotomy team rather than any direct change to patient care.
- 2) **Decision support**. This includes:
  - a. A visual clinical support tool (appendix) urging the clinical team to minimize laboratory assessments and optimize patient bleeding risk. This will be available by the clinical workstations for the ICU team and at the patient's bedside.
  - b. A daily rounding checklist (appendix) accompanied by brief daily discussion (2-minutes) between trained study coordinators and the ICU care team during clinical rounds to reiterate the purpose of the study. The checklist will be available at the clinical workstations for the ICU team.
  - c. Epic direct messages sent twice per day (targeting day and night providers) with the information from the visual support tool to reiterate the purpose of the study.
- 3) **Pharmacologic anemia treatment**. These therapies will be given immediately following enrollment and targeted to 2 broad groups:
  - a. Anemias responsive to iron supplementation alone. This includes patients with anemia secondary to acute blood loss  $\geq$  500 ml and patients with iron deficiency anemia (i.e. ferritin  $<100$  ng/ml or transferrin saturation  $<20\%$ ).
    - Patients with iron-responsive anemias will receive a single total dose infusion (1000 mg) of intravenous (IV) low molecular weight iron dextran (INFeD)
    - This medication is diluted in 500 ml of 0.9% saline. A 25 mg test dose (12.5 ml) is administered over 5 minutes to ensure no immediate hypersensitivity reaction, followed by the completion of the infusion over 1-2 hours (not to exceed 1000 mg/hr). This medication will be given in accordance with Mayo Clinic administration guidelines.
  - b. Anemias requiring erythropoietic stimulation. This includes anemia not secondary to acute blood loss or iron deficiency (e.g. anemia of inflammation, anemia of renal disease). Etiology will be determined immediately *prior to randomization* upon review of laboratory values (i.e. iron studies) and clinical history (i.e. admission diagnoses, surgery/acute blood loss) with treatment decisions adjudicated pre-randomization by the PI and trial Co-I's should the PI be unavailable.
    - Patients without iron-responsive anemias will receive a single dose of 40,000 units of subcutaneous EPO (Retacrit). For those with ferritin less than 1000 ng/ml they will also receive 1000 mg IV iron prior to EPO administration to replenish usable iron, given that iron will

invariably be mobilized secondary to EPO stimulation. EPO will be given in accordance with Mayo Clinic administration guidelines.

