The third component of the clinical intervention is the utilization of EPO and/or iron for the treatment of anemia, which does carry tangible patient risks. **Iron** will be administered as a single 1000 mg dose of IV low molecular-weight iron dextran. This is an approved therapy for patients with iron-deficiency anemia that is utilized in current clinical practice for critically ill patients with anemia and contraindications to transfusion therapies (i.e. Jehovah’s witness patients) and post-surgical patients after large volume blood loss. The estimated incidence of SAEs with newer IV iron formulations, such as low molecular weight iron dextran, is less than 1 in 250,000 administrations. Nevertheless, immediate risks of IV iron are real and include allergic reactions (<1%) and non-allergic infusions reactions (e.g. myalgias, arthralgias, dizziness, <1%). Additionally, as a long-term risk, repeated doses of iron administration, particularly to patients with iron storage disorders (i.e. hemochromatosis) or those requiring frequent and recurrent RBC transfusions, can culminate in iron overload. Patients with hemochromatosis or elevated iron stores (i.e. ferritin > 1000 ng/ml) will not be eligible to receive iron therapies in this study.

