alone; hence, the potential benefits of IV iron in this group are high while the potential harms of EPO administration (e.g. thrombosis) likely outweigh any incremental benefit on hemoglobin recovery. Further, IV iron will be given as a single total dose infusion, which provides complete restoration of usable iron for >4 weeks. For anemias requiring erythropoietic stimulation, EPO will be given as a single 40,000 unit dose after ensuring restoration of iron stores, a strategy that has resulted in sustained hemoglobin improvement and is widely used in anemia clinics. Patients with laboratory evidence (i.e. ferritin > 1000 ng/mL) or clinical conditions (i.e. hemochromatosis) indicating states of iron overload will not receive iron supplementation prior to EPO therapy. A single EPO dose carries a lower risk for thrombotic complications than repeat dosing, which is particularly relevant in the critically ill.

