
Regarding EPO, several actions are being taken to mitigate risk: 1) excluding patients with relative contraindications to EPO therapy (e.g. pregnancy, active thrombosis, an inability to receive VTE pharmacoprophylaxis, active myocardial ischemia, poorly controlled hypertension, recent stroke); 2) tailoring pharmacotherapy to anemia etiology, such that EPO is not administered to patients that are likely to mount an appropriate erythropoietic response with iron therapy alone; and 3) providing only a single dose of EPO therapy for those receiving this therapy. Of note, the optimal dosing of EPO is unknown in the critically ill, though clinical trials in surgical patients have shown that a single dose of EPO results in sustained hemoglobin improvement. All adverse events will be closely evaluated by study personnel as outlined in the data safety monitoring plan. Similar to iron, EPO will be administered by critical care nurses in accordance with institutional medical administration protocols. Iron will be co-administered immediately prior to EPO to ensure adequate iron stores for EPO-induced augmentation of bone marrow erythropoiesis. Patients will be continuously monitored at the time of administration for immediate adverse effects (e.g. cutaneous reactions, hypertension, dizziness, nausea). Those without immediate reaction will be observed clinically for 1 hour post-infusion for the

development of delayed reactions with blood pressure measurements at least every 15 minutes, continuous pulse oximetry, and telemetry. Those experiencing infusion reactions will be observed for longer times as dictated by the severity of the reaction.

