Patients satisfying inclusion/exclusion criteria, or their legal proxies, will be approached by trained study coordinators for written informed consent. Participants will be randomized 1:1 to active intervention vs. standard care using a stratified permuted block design by anemia etiology (iron-responsive or not) and ICU admission indication (surgical vs. non-surgical). The intervention arm is multi-faceted with 3 primary components: 1) **Optimized phlebotomy**, defined by minimal volume draws (i.e. 0.1-2 ml vs. standard 3-10 ml per laboratory order) and closed-loop blood sampling (eliminates 10 ml waste volume per draw), all performed by a dedicated phlebotomy team independent from the treatment team; 2) **Decision support aids**, including visual and electronic alerts reminding the care team to minimize non-essential laboratory testing and mitigate patient-specific bleeding risk (e.g. stress ulcer prophylaxis in high-risk patients); and 3) **Pharmacologic anemia treatment** (given immediately following enrollment when hemoglobin first observed <10 g/dL) targeted to 2 broad groups: 1) anemias responsive to iron supplementation alone (i.e. acute blood loss, true iron deficiency [i.e. ferritin <100 ng/ml, transferrin saturation < 20%]), and 2) anemias requiring erythropoietic stimulation (e.g. anemia of inflammation, anemia of renal disease). Etiology of anemia will be determined immediately prior to randomization upon review of laboratory values (i.e. iron studies) and clinical history (i.e. admission diagnoses, surgery/acute blood loss) with treatment decisions adjudicated pre-randomization by the PI or Co-I's. Subjects then randomized to the intervention arm will receive pharmacologic anemia treatment in accordance with their anemia etiology. Patients with anemias responsive to iron supplementation will receive a single total dose infusion (1000 mg) of intravenous (IV) iron dextran. Patients with anemias requiring erythropoietic stimulation will receive a single dose of 40,000 units of subcutaneous EPO, which will be immediately preceded by 1000 mg of IV iron dextran to replenish usable iron stores if the ferritin level is < 1000 ng/ml. All patients randomized to the intervention group will receive

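### Sections 4.1 and 6.1.1 order 1000 mg IV iron for every iron-responsive patient without the iron-overload bar of 2.3.1, and applying that bar leaves such a patient with no assigned drug

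*Combined protocol and SAP*

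**What the plan says.** Section 2.3.1 sets the bar for the whole study: "Patients with hemochromatosis or elevated iron stores (i.e. ferritin > 1000 ng/ml) will not be eligible to receive iron therapies in this study". It is not limited to one etiology group.

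The orders for the iron-responsive group do not carry it. Section 4.1 states: "Patients with anemias responsive to iron supplementation will receive a single total dose infusion (1000 mg) of intravenous (IV) iron dextran". Section 6.1.1 (3a) repeats the order: "Patients with iron-responsive anemias will receive a single total dose infusion (1000 mg) of intravenous (IV) low molecular weight iron dextran (INFeD"). Section 6.1.2 adds that dosing is not tailored to the individual patient.

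The orders for the EPO group carry part of it. In 4.1 the EPO dose is to be "immediately preceded by 1000 mg of IV iron dextran to replenish usable iron stores if the ferritin level is < 1000 ng/ml", and 6.1.1 (3b) has the same ferritin check: "For those with ferritin less than 1000 ng/ml they will also receive 1000 mg IV iron prior to EPO administration". Neither mentions hemochromatosis. Section 2.3.3 does: patients with laboratory evidence or "clinical conditions (i.e. hemochromatosis) indicating states of iron overload will not receive iron supplementation prior to EPO therapy".

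On who receives EPO, 6.1.1 (3b) says: "Patients without iron-responsive anemias will receive a single dose of 40,000 units of subcutaneous EPO (Retacrit"). Section 2.3.3 explains that therapy is tailored so that "EPO is not administered to patients that are likely to mount an appropriate erythropoietic response with iron therapy alone". Section 4.1 nevertheless says that everyone in the intervention arm gets iron, EPO or the two together.

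**The concern.** A reader dosing from 4.1 or 6.1.1 alone would give iron to a patient whom 2.3.1 declares ineligible for it. A reader who applies 2.3.1 withholds the iron and then finds no instruction on what replaces it, if anything. The statement in 4.1 that all intervention patients receive a drug could push that reader toward EPO, which 2.3.3 and 4.1 both argue against for this group.

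What is at stake is patient safety and consistent treatment of like patients. There is also a bookkeeping consequence. Section 6.4 measures compliance by receipt of drug, and 7.2 allows replacement of randomized subjects who did not receive the intervention. A patient correctly denied iron would look non-compliant, and the plan does not say whether that patient could be replaced.

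**Working it through.** No statistical figure is at issue, so the check sets the sections side by side.

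**Can the case arise?** Yes. Under 6.1.1 (3a), acute blood loss of at least 500 ml makes a patient iron-responsive at any ferritin. So does transferrin saturation below 20% on its own, because the two laboratory criteria are joined by an *or*. None of the 12 exclusion criteria in 5.2, and none of the 10 rows of the exclusion table in 2.3.3, names hemochromatosis or high ferritin.

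**Where is the bar written?**

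| Section | Ferritin limit of 1000 ng/ml | Hemochromatosis |
|---|---|---|
| 2.2 | yes, for iron given with EPO | no |
| 2.3.1, iron paragraph | yes, any study iron | yes, any study iron |
| 2.3.1, EPO paragraph | yes, for iron given with EPO | no |
| 2.3.3 | yes, for iron given with EPO | yes, for iron given with EPO |
| 4.1 | yes, for iron given with EPO | no |
| 6.1.1 (3b) | yes, for iron given with EPO | no |
| 6.1.1 (3a) | no | no |

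The ferritin limit stands in 6 places. In 5 of them it governs only iron given with EPO, so 6 − 5 = 1 place (the iron paragraph of 2.3.1) covers the iron-responsive patient. The hemochromatosis bar stands in 2 places, both in the risk section and neither in a dosing section.

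**Illustrative case A: 800 ml blood loss, ferritin 1500 ng/ml.**
1. The loss exceeds 500 ml, so the patient is iron-responsive.
2. Sections 4.1 and 6.1.1 (3a) order 1000 mg iron.
3. Section 2.3.1 bars it, since 1500 > 1000.
4. Section 6.1.1 (3b) gives EPO only to patients who are not iron-responsive, so EPO is not assigned.
5. Section 4.1 says the patient receives at least one of the two drugs.

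Giving iron breaks 2.3.1, giving EPO breaks 6.1.1 (3b), and giving neither breaks 4.1.

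**Illustrative case B: no bleeding, hemochromatosis, ferritin 400 ng/ml, transferrin saturation 40%.**
1. Ferritin is not below 100 ng/ml and saturation is not below 20%, so the patient belongs to the EPO group.
2. Because 400 < 1000, 4.1 and 6.1.1 (3b) order iron before EPO.
3. Sections 2.3.1 and 2.3.3 withhold the iron, and EPO alone remains.

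Here the answer is settled. The dosing text merely omits the hemochromatosis check.

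**How many patients?** The documents give no distribution of ferritin, saturation or hemochromatosis. With 100 randomized 1:1, about 100/2 = 50 are in the intervention arm. If a share q of them is both iron-responsive and barred (purely an assumption), the expected number is 50q and the chance of at least one is 1 − (1 − q)^50:

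| Assumed q | Expected number | Chance of at least one |
|---|---|---|
| 1% | 0.5 | 39% |
| 2% | 1 | 64% |
| 5% | 2.5 | 92% |
| 10% | 5 | 99% |

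This range shows only that a small share would be enough to produce a case. It is not an estimate.

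**The case against.** The strongest reply is that the bar already exists. Section 2.3.1 states it for the whole study, and a categorical safety rule need not be repeated beside every dose. Iron studies and history are reviewed, and treatment adjudicated by the PI or a Co-I, before randomization. Criterion 12 of 5.2 lets the clinical team object, and iron is given under institutional guidelines that are not in the documents. Most cases would probably be caught. This stands in part: a reader might infer that the trial has no safeguard against iron overload, and the documents do not support that. The defect is that the dosing sections omit the safeguard and in the iron-responsive branch contradict it. Adjudication sorts patients into two groups but supplies no rule for someone who belongs in the iron group and may not have iron.

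A second reply is that 4.1 settles the matter in favor of EPO by elimination, because a patient who cannot have iron is not plainly one who would respond to iron alone. The wording in 2.3.3 leaves that room, and the remark in 4.1 on EPO's harms is rationale rather than prohibition. But 6.1.1 (3b) assigns EPO by etiology, and 2.3.3 and 4.1 both judge the balance unfavorable in this group. Criteria 6, 7 and 10 of 5.2 are also waived for acute blood loss, so a barred bleeding patient may have recent thrombosis, acute coronary syndrome or ischemic stroke, or be unable to receive thromboprophylaxis. EPO should not be reached by inference.

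A third reply is that the EPO-branch gap is only an unrepeated rule. That stands: 2.3.3 covers it, and it warrants a matching edit and no more.

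**Conclusion.** The plan is wrong as written. Two dosing sections order a drug that the risk section forbids for an identifiable and enrollable patient. Applying the prohibition then contradicts the statement that every intervention patient receives a drug.

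The safety relevance is minor to moderate. Exposure is a single dose, 2.3.1 links iron overload to repeated dosing, and pre-randomization review would probably intercept most cases. How often it would arise cannot be judged from the documents. The conflict itself is certain, because it rests only on the text.

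A reader might infer that the efficacy result is compromised. The documents do not support this: etiology is fixed before randomization in both arms and is a stratification factor, and analysis is by allocated arm, so the 1-month hemoglobin comparison is not biased. The sample size and alpha are untouched. The reason to correct the text is safety and consistency of treatment.

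The definition of acute blood loss, which has a volume in 6.1.1 and none in 5.2, is a separate matter and is not part of this conclusion.

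**What to change.** 1. In 6.1.1 (3a) and the matching sentence of 4.1, make the iron order conditional: no iron if ferritin exceeds 1000 ng/ml or the patient has hemochromatosis.
2. In 6.1.1 (3b) and the EPO sentence of 4.1, add hemochromatosis to the ferritin check, so that both agree with 2.3.3.
3. State that an iron-responsive patient barred from iron receives optimized phlebotomy and decision support without drug, and does not receive EPO.
4. Amend the statement in 4.1 that all intervention patients receive a drug, and say in 6.4 and 7.2 how such a patient counts for compliance and replacement.

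The cost is a few sentences. Iron studies and clinical history are already reviewed before randomization, so nothing further is collected. The drawback is that some intervention patients, in unknown and possibly zero number, receive no drug. Excluding them in 5.2 would also close the gap, but would shrink the eligible pool by an amount the documents do not allow one to estimate.
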